Multiple criteria or multicriteria decision analysis (MCDA) – also known as multiple criteria decision making (MCDM) – is the collective name of formal approaches that support decision making by taking into account multiple criteria in an explicit and transparent way. The methodology of MCDA has extensively been used in various disciplines, but given their increased complexity as compared to other methods, they have not been as used in healthcare. Swing weighting is a MCDA method and takes the criteria levels into account when estimating criteria weights. Patients are first exposed to a hypothetical worst-case scenario, where all attributes of preference are set to the worst possible levels. They are then asked to identify the most important criterion to them by selecting the one that, if improved, would improve the overall situation the most. The most important criterion is assigned 100 points, and then decision-makers are asked about the next criterion to be moved from its worst level to its best – that will receive a point value <100. Different options (e.g. treatments) are then scored against each criterion and the weights are used to summarize scores for the purposes of comparing these options. The options (e.g. treatments) are then scored against each criterion and the weights are used to summarize scores for the purposes of comparing these options.

4.1.2.6.

Variables

The web-based survey will include the following sections and variables:

- A DCE exercise to evaluate PP and estimate utilities;
- A short TTO exercise to evaluate health valuation utilities (subset of patients);
- A MCDA exercise to evaluate PP and estimate utilities (subset of patients);
- A ranking exercise in which respondents will be asked to rank order the attributes;
- A set of questions regarding:
 - Respondents' socio-demographics, clinical (.e. diagnosis, cancer stage, number of previous treatments), self-assessed health status, constructs related to choices that

Template No.: PCE_TP_CSC0016 Revision 2 Reference:

PCE_OP_CSC0014

Effective Date: 15Dec2019

may explain heterogeneity (i.e. age, disease severity, family background, patient's understanding of the disease, health awareness and literacy);

- Question to assess respondents' level of understanding of the DCE, MCDA/TTO tasks;
- Question to assess how difficult respondents found to complete the DCE, MCDA/TTO tasks

Sample

Study Eligibility Criteria

4.2.

4.2.1.

Qualitative Evidence Generation

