To complement the analysis for this primary objective, cancer PP about the benefits and harms of cancer therapies and the different trade-offs between factors will also be examined using MCDA and TTO methodologies with a smaller subset of patients. For the MCDA method, partial value functions will be elicited using the additive value model. Ratings of the alternatives will be described, along with the sum of the preference weights to account for relative importance, using frequencies and related percentages. The sum and spread of the weights will be described using a non-linear curve representing the average weights as a function of the ratings. For the TTO method, regression analysis will be applied to estimate utility values by dividing the number of years corresponding to the patient's choices for a treatment by 10 (years). The patient's preferences with different treatments will be measured in units of quality of life differences between the two treatment options, and the utility values (mean, SD, 95% confidence intervals) will range between 0 and 1.

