Bayesian MNL models will also be used to control for differences in error variance and explore consistency of treatment choices for the DCE methodology. Random utility theory assumes that there may be an additional component of utility that is unobservable. Therefore, the utility function comprises of two elements: a deterministic component based on the participants' preferences for the observed attributes of the alternative, and random error associated with the alternative. ^[46] In the MNL model, it is assumed that choice questions measure utility equally well (or equally poor) across all participants and choice tasks. However, if the variance is not constant across all participants or choice tasks, differences in model estimates between participants or choice tasks may appear different and could lead to biased results. It is therefore important to control for error variances. Regression models will aim to be conducted to examine the relationship between the utilities from the MCDA and TTO methods and patients' understanding and differences when completing the choice tasks, using regression coefficients and 95% confidence intervals. Regression assumptions will be assessed, and appropriate regressions models will be based on the assumptions and data distributions of the utilities.

Exploratory Analyses

An additional objective is to compare and contrast preference weights and patient associations with stated preference using different stated preferences methods. Preference weights estimated from the three methods and association between preferences and patients' characteristics will be compared both descriptively and using anchor-based mapping regressions. Mapping predicts HRQoL states by statistically relating DCE scores to MCDA and TTO scores using a regression mapping method. The aim is for coefficients for each attribute to be calculated by multiplying the DCE coefficients by MCDA and TTO scores in separate regression models. The regression assumptions of the utilities for each method will first be examined and will aim to use appropriate models based on the assumptions and data distributions. Scatterplots of the residuals for the utilities from each method will be further examined. If the utilities violate assumptions and data distributions for regression, transformations may be considered. Otherwise, non-parametric techniques will be used.

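### The planned curve of average MCDA weights against option ratings cannot describe the weights and should give way to a per-attribute summary

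*Protocol*

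**What the plan says.** The Protocol describes the MCDA in two places.

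The method is in the section headed Multiple Criterion Decision Analyses (MCDA), which says "Swing weighting is a MCDA method and takes the criteria levels into account when estimating criteria weights". The patient starts from a worst case on all attributes and picks the criterion whose improvement matters most, which receives 100 points. Then "decision-makers are asked about the next criterion to be moved from its worst level to its best", and that criterion receives fewer than 100 points. Scoring comes afterwards: "Different options (e.g. treatments) are then scored against each criterion and the weights are used to summarize scores".

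The analysis is in section 5.2, under Primary Analysis, where MCDA and time trade-off (TTO) complement the main method, the discrete choice experiment (DCE). Three consecutive sentences cover MCDA:

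- The first names the model and says that "partial value functions will be elicited using the additive value model".
- The second concerns how the treatment options are rated. It also reports summed weights as a gauge of relative importance, with a categorical summary (frequencies and percentages) for both.
- The third fixes the display at issue here: "The sum and spread of the weights will be described using a non-linear curve representing the average weights as a function of the ratings".

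The opening of the same Primary Analysis section sets a general rule: continuous variables get mean, SD, 95% CI, median, quartiles and range, and categorical variables get frequencies and percentages. Full detail is left to the statistical analysis plan. Under Exploratory Analyses, "Preference weights estimated from the three methods" are compared descriptively and by mapping regressions.

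**The concern.** In an additive value model each patient has one weight per criterion, fixed by the swing task. The part that may be non-linear is the partial value function, which relates value to the level of an attribute. The quoted curve puts the weight on the vertical axis and the rating of an option on the horizontal axis, so it treats an input of the model as a function of its output. It is also meant to convey the sum and the spread of the weights, and a line of averages does neither.

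At stake is the figure by which 450 patients' MCDA weights are to be described. Readers would take its slope as a finding about preferences when it may reflect which options were put up for rating. The neighbouring sentence adds to the problem, because it applies a categorical summary to swing weights, which are continuous.

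**Working it through.** The Protocol gives no figure for this analysis, so there is nothing to reproduce. The check is a comparison of the passages, some algebra, and an illustration.

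**1. Order of steps.** In the MCDA method section the order is swing weights, then option scores, then weighted sum. In the Primary Analysis text the weight is displayed as a function of the rating. The two run in opposite directions.

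**2. Model.** For option a and criteria i, V(a) = Σ w_i · v_i(a). The w_i are constants for a patient. Only v_i can bend.

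**3. Sum and spread.**
- Normalised weights are w_i = points_i / Σ points, so Σ w_i = 1 for every patient and the sum carries no information.
- With raw points and k criteria the sum lies between 100 and 100·k, and reflects how a patient uses the point scale.
- If the sum is taken over patients for one criterion, it equals n times the mean and adds nothing to the mean.
- In each case a curve of average weights leaves out the between-patient SD.

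**4. Dependence on the alternative.** Take three criteria, normalised weights and linear partial values.
- Option A scores 0.9, 0.5, 0.1: V = 0.9w₁ + 0.5w₂ + 0.1w₃ = 0.5 + 0.4(w₁ − w₃).
- Mirror option B scores 0.1, 0.5, 0.9: V = 0.5 − 0.4(w₁ − w₃), which is 1 minus the rating of A.
- Option C scores 0.6 throughout: V = 0.6 for every patient.

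So any trend of w₁ against the rating of A is exactly reversed for B, and for C no curve exists.

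**5. Illustration.** Only the 450 patients come from the Protocol. The rest is assumed: three criteria; three uniform draws from 10 to 100 per patient, the largest replaced by 100; random allocation to criteria; normalisation to 1; overall rating taken as the weighted score. The same 450 weight vectors are used in every row.

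| Alternative rated | Mean w₁ by rating quartile, low to high | Correlation of w₁ with rating |
|---|---|---|
| A, linear | 0.176, 0.246, 0.341, 0.552 | +0.86 |
| B, linear | 0.552, 0.341, 0.246, 0.176 | −0.86 |
| A, square-root values | 0.182, 0.253, 0.348, 0.532 | +0.78 |
| B, square-root values | 0.564, 0.352, 0.234, 0.164 | −0.92 |
| C | rating constant, no curve | none |

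If the rating is instead a score on criterion 1 alone, drawn independently of the weights, mean w₁ in four equal score bands is roughly flat: 0.337, 0.345, 0.310, 0.322.

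**6. Direct summary of the same weights.** The means are 0.329, 0.332 and 0.339, and the SDs 0.171, 0.177 and 0.181. For criterion 1 the 95% CI is 0.329 ± 1.96 × 0.171/√450 = 0.329 ± 0.016, or 0.313 to 0.345. No alternative enters this calculation, so it is the same whichever options are rated.

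**The case against.** The strongest reply is that this is one poorly worded descriptive display for a complementary method. Four parts of that reply stand.

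- **Intervals.** A reader might infer that the MCDA weights get no interval. The Protocol does not support that. Swing points are continuous, and section 5.2's general rule gives continuous variables a mean, SD and 95% CI. What remains is an inconsistency with the sentence that uses frequencies and percentages.
- **Scope.** A reader might take the curve to be the whole MCDA result, or think that without it MCDA cannot enter the comparison of methods. Neither follows. Ratings and summed weights are also described, regressions on MCDA utilities are planned, and nothing under Exploratory Analyses takes the curve as an input.
- **Contradiction.** A reader might say that the curve contradicts the additive model. That is too strong. The illustration is fully additive and still yields such curves, as a product of the option chosen. Non-linearity is no conflict either, since partial value functions may be non-linear, and the sentence may be a garbled account of them.
- **Numbers.** The option sets are invented, and mirroring them forces the sign to change. They show that the curve can depend on the options, not what this study would find.

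The appeal to the statistical analysis plan does not stand. The Protocol does not leave the summary open. It names a particular one that does not do what is asked of it, and a later plan would inherit it.

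**Conclusion.** Wrong as written, but limited to one summary of a complementary method. The curve reverses the order of the Protocol's own swing-weighting procedure. It cannot show the spread of the weights, nor any useful sum once they are normalised, and its shape can reverse or vanish while preferences stay the same. The reversal and the constant case follow from algebra under an additive model with normalised weights and linear partial values. The sizes in the table rest on the assumed weights and options and are illustrative only. Because the sentence leaves unclear whether the rating is overall or per criterion, the actual shape cannot be predicted. The DCE analysis is unaffected, and the weights remain usable for the exploratory comparison.

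**What to change.** In the MCDA paragraph of section 5.2:

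1. Delete the curve of weights against ratings.
2. Report each attribute's normalised swing weight across the MCDA patients (planned n = 450) as mean, SD, 95% CI and quantiles, in line with the section's general rule. Keep frequencies and percentages for categorical quantities.
3. Show partial value functions separately, as value against attribute level, one panel per attribute. If intermediate levels are not rated, state that value is assumed linear between worst and best, and compare MCDA with DCE only over the full worst-to-best range.

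The cost is a few sentences and a different figure. The weights are collected in any case, so no new data are needed.

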5.2.2. Secondary Analyses

5.2.2.1.

Secondary Analysis

The secondary objective is to determine the extent to which patients' heterogeneous characteristics are associated with stated preferences. To explore variation in preferences for patient treatment based on patient factors collected (cultural characteristics, demographic characteristics, clinical (time of diagnosis, disease stage, treatment experience), psychological characteristics (cognition, health literacy, health numeracy, health attitudes); Bayesian MNL models will be conducted with coefficients for attribute-levels interacting with clinical variables (e.g. cancer type, level of experience) and socio-demographic variables (e.g. age, sex, country, education level) for the DCE methodology. Regression models will also be conducted to examine the relationship between the utilities from the MCDA and TTO methods and patients' characteristics, using regression coefficients and 95% confidence intervals. Regression assumptions will be assessed, and appropriate regressions models will be based on the assumptions and data distributions of the utilities.

Template No.: PCE_TP_CSC0016 Revision 2 Reference:

PCE_OP_CSC0014

Effective Date: 15Dec2019

Bayesian MNL models will also be used to control for differences in error variance and explore consistency of treatment choices for the DCE methodology. Random utility theory assumes that there may be an additional component of utility that is unobservable. Therefore, the utility function comprises of two elements: a deterministic component based on the participants' preferences for the observed attributes of the alternative, and random error associated with the alternative. ^[46] In the MNL model, it is assumed that choice questions measure utility equally well (or equally poor) across all participants and choice tasks. However, if the variance is not constant across all participants or choice tasks, differences in model estimates between participants or choice tasks may appear different and could lead to biased results. It is therefore important to control for error variances. Regression models will aim to be conducted to examine the relationship between the utilities from the MCDA and TTO methods and patients' understanding and differences when completing the choice tasks, using regression coefficients and 95% confidence intervals. Regression assumptions will be assessed, and appropriate regressions models will be based on the assumptions and data distributions of the utilities.

Exploratory Analyses

An additional objective is to compare and contrast preference weights and patient associations with stated preference using different stated preferences methods. Preference weights estimated from the three methods and association between preferences and patients' characteristics will be compared both descriptively and using anchor-based mapping regressions. Mapping predicts HRQoL states by statistically relating DCE scores to MCDA and TTO scores using a regression mapping method. The aim is for coefficients for each attribute to be calculated by multiplying the DCE coefficients by MCDA and TTO scores in separate regression models. The regression assumptions of the utilities for each method will first be examined and will aim to use appropriate models based on the assumptions and data distributions. Scatterplots of the residuals for the utilities from each method will be further examined. If the utilities violate assumptions and data distributions for regression, transformations may be considered. Otherwise, non-parametric techniques will be used.

Patients will also be asked about the level of difficulty completing each task (either DCE/MCDA or DCE/TTO). This question will be asked at the end of the survey, and the data will be compared descriptively. Continuous variables will be described by mean, standard deviation (SD), 95% confidence intervals (CI), median, 25th and 75th percentiles, minimum and maximum. Categorical

Template No.: PCE TP CSC0016 Revision 2 Reference:

PCE OP CSC0014

Effective Date: 15Dec2019

variables will be described by frequencies and related percentages of the study population, and by subgroups.

For the quantitative phase, all computations and generation of tables, listings and data for figures will be performed using Statistical Analysis System (SAS)® version 9.2 or higher (SAS Institute, Cary, NC, USA).

6. Storing and Archiving of Data

At the close of the study, all patient records will be archived in an access-controlled file for the period of 5 years from end of study.

7. Ethical and Regulatory Obligations

IRB Process & Informed Consent

7.1.

In accordance with local regulations and the ethical principles that have their origin in the principles of the Declaration of Helsinki, all patients must provide informed consent, or agreement to a data protection notice (DPN) before entering into the study. In the qualitative phase, all patients will be asked to provide verbal consent to participate in the interview. In the quantitative online survey phase, patients will provide their agreement to the DPN to be enrolled and continue with the online survey. Online consent or agreement to a DPN will be obtained prior to being granted access to the survey. Patients in either phase will be allowed sufficient time to consider participation in the study. By agreeing to the DPN, patients will consent to their data being used in the study unless they withdraw voluntarily afterwards for any reason.

In order to maintain patient confidentiality, patients in the qualitative interviews and the quantitative survey will be assigned a unique identifier upon study enrollment. This identifier will be used for the purpose of data analysis and reporting. All parties will ensure the protection of personal data and will not include names on any study forms, reports, publications, or in any other disclosures, except where required by law. Patients will be informed about data handling procedures and asked for their consent. Data protection and privacy regulations will be observed in capturing, forwarding, processing, and storing patient data. Patient information will always be kept in a separate and encrypted database only accessible to the research team for the purposes of scheduling patient interviews. Every effort will be made to protect patient confidentiality according to the Directive 95/46/EC on the protection of individuals, and in compliance with Safe Harbor privacy principles.

Template No.: PCE TP CSC0016 Revision 2 Reference:

PCE_OP_CSC0014

Effective Date: 15Dec2019

Consistent with local regulations, a study protocol and patient facing material will be submitted to central Ethics Committees active in the countries of interest for its review.

Potential Risks and Limitations

There are no expected risks to patients as a result of involvement in this study. Their regular medical care will not change as a result of participating in this study and this study should not 7iAvolve any physical risk.

There may be non-physical risks and limitations associated with taking part in different phases of the study, such as:

Qualitative Evidence Generation

- Information bias: All data collected depends on patient report and recall. Self-reported 7.2.1. preferences may also differ from observed or actual preferences. The IQVIA moderators will be fully trained on the study protocol, interview guide and good practice guidelines. Thematic coding of the transcripts will be recorded when patient verbatim is spontaneously reported or prompted.
 - Selection bias: Generalizability is generally not sought in qualitative studies but rather recruitment of a diverse sample to provide varied insights. Efforts will be made to recruit a diverse sample of patients for the qualitative phase. Patient characteristics will also be fully described as per the patient screener.
 - Burden to the patient: Reflecting on and trading off different treatment attributes of relevance may be overly cognitively burdensome to the patient. To minimize this risk, feedback on the qualitative interviews and identification of the attributes will be assessed using cognitive debriefing techniques.

7.2.2.

Quantitative Evidence Generation

• Information bias: As with collection of all self-report data, there is a possibility that patients may give inaccurate responses based on the method of survey administration. Using an anonymized online survey may reduce this type of bias compared to interview-based methods as risk of social desirability bias is minimized in the absence of a researcher, and in the knowledge that responses will not be linked back to individuals. This will be emphasized in the survey instructions to encourage accurate and truthful responses from

Template No.: PCE TP CSC0016 Revision 2 Reference:

PCE_OP_CSC0014

Effective Date: 15Dec2019

patients in this phase of the study. However, self-reported preferences may still differ from observed or actual preferences for reasons that cannot be controlled for in this study

- Selection bias: Study participation is voluntary, and the sample of patients recruited could
 differ those from the general population. Efforts will be made to ensure the recruitment of
 patients is as generalizable as possible. Information will be retained on patients not
 meeting selection criteria for enrollment. Patient characteristics will also be fully described
 as per the patient screener.
- Attributes identified and captured in the current study: There may be treatment attributes and factors outside of the current study that are important to patients but were not identified and represented in this study. There is also the risk that patients may not relate or understand certain attributes. Our attributes and associated-levels in the preference survey will be based on the targeted literature review and feedback received from patients during the qualitative evidence generation interviews. To minimize this risk, relative importance of attributes and associated-levels will be assessed. Patients will also be asked questions on how well the patients understood the attributes described in the choice tasks.
- Burden to the patient: The administration of the different PP methodologies and trading
 off different treatment attributes of relevance may be overly cognitively burdensome to the
 patient. To minimize this risk, patients will be informed how far they have completed the
 survey by including a progress bar in the survey.

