The primary objective is aimed at identifying and describing the cancer PP about benefits and harms of cancer drugs and to understand the trade-offs between factors leading to PP with the main method, DCE. For this objective, we propose using Bayesian multinomial logistic regression (MNL) models reporting odds ratio's and 95% confidence intervals. Attribute-levels will be estimated relative to a reference level for each attribute. The reference level will be selected based on the attribute-level having the lowest parameter estimate. The analysis of preferences of patients towards a treatment will allow us to investigate which attributes (and levels) influence patient choices for selecting the most appropriate treatment for patients with various cancers. A Bayesian MNL model computes the best fitting estimates via utility estimation to account for the overall pattern of choices reported by the patients. Results from utility estimation allows for the estimation of coefficients for each attribute-level, with a positive parameter in the model representing a positive utility associated with a particular attribute-level, whereas a negative parameter in the model represents disutility associated with a particular attribute-level. Using a Bayesian MNL model, the coefficients for the different attribute-levels can then be combined to allow for investigation of these factors when making a treatment decision. [41]

The relative importance of the attributes that are relevant to the patients' preference for selecting treatment will be also assessed depending of the stated preference method used. Generally,

Template No.: PCE TP CSC0016 Revision 2 Reference:

PCE OP CSC0014

Effective Date: 15Dec2019

mean part-worth utility values for each attribute will be estimated using the Bayesian MNL models for the main method DCE. Part-worths will be scaled and normalized to allow for comparisons to assess the relative importance of the attributes from most important to least important. The reference factor level will be set to the least important value for each attribute. The factor level with the largest part-worth (in absolute value) would also represent the impact of that attribute it belongs to.^[45] The relative importance of the attributes will be described in related percentages.

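### The protocol relies on a multinomial logit to control unequal error variance, which that model assumes away, so subgroup interactions can mistake choice noise for preference

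*Protocol*

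**What the plan says.** For the discrete choice experiment (DCE), the Primary Analysis part of Section 5.2 names one model family: "we propose using Bayesian multinomial logistic regression (MNL) models reporting odds ratio's and 95% confidence intervals". It also plans to normalise the part-worths and express each attribute's relative importance as a percentage.

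The secondary objective asks how far patient characteristics are associated with preferences. Section 5.2.2.1 answers it with the same family: "Bayesian MNL models will be conducted with coefficients for attribute-levels interacting with clinical variables", and also with socio-demographic variables, for which age, sex, country and education level are the examples. Psychological factors such as cognition, literacy and numeracy stand in the preceding list of factors to explore. They are not among the named interaction terms.

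The next paragraph of that section makes four statements in turn:

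1. "Bayesian MNL models will also be used to control for differences in error variance and explore consistency of treatment choices for the DCE methodology".
2. "In the MNL model, it is assumed that choice questions measure utility equally well (or equally poor) across all participants and choice tasks".
3. If the variance is not constant, "differences in model estimates between participants or choice tasks may appear different and could lead to biased results".
4. "It is therefore important to control for error variances".

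Section 4.1.2.6 collects how well patients understood the tasks and how hard they found them. Section 5.2.2 then relates understanding only to the MCDA and TTO utilities and compares difficulty descriptively. Neither is said to enter the DCE model. Section 5.2 leaves the full description of the analyses to the statistical analysis plan, which is not at hand.

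**The concern.** Statements 1 and 2 cannot both serve the purpose of the paragraph. The model offered as the remedy is the one said to rest on the assumption that needs relaxing. The protocol identifies the problem correctly, says what it can do to the results, commits to controlling it, and then names a tool that cannot.

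The secondary DCE analysis is at stake. In a logit, preference and error variance enter only as a product. If one group of patients answers less consistently, all of its coefficients shrink towards zero and all of its odds ratios towards 1. An attribute-by-group interaction then picks up the shrinkage and shows it as a difference in preference. Education, age and country are named interaction variables and could plausibly go with differences in choice consistency.

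**Working it through.** The protocol gives no figure to reproduce. The check is one of model logic, followed by a simulation to show the size of the effect.

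**Logic.** Let a patient in group g choose between profiles A and B, with preference weights β and scale λ_g (the inverse of the error standard deviation, up to a constant):

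P(A) = 1 / (1 + exp(−λ_g · β′(x_A − x_B)))

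Only the product λ_g·β can be estimated. The MNL sets λ_g = 1 for everyone. With group 1 at scale 1 and group 2 at scale s, and the same β in both, an attribute-by-group interaction estimates s·β − β = (s − 1)·β. That is not zero unless s = 1. A Bayesian prior on β leaves λ_g fixed, so the word Bayesian does not help.

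**Inputs from the protocol.** About 900 patients and two alternatives per task.

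**Assumed inputs (not in the protocol).** A covariate that splits the sample 450/450; 8 or 12 tasks; five two-level attributes with coefficients 0.8, 0.6, 0.4, 0.3 and 0.2, identical in both groups; scale ratio s of 1.0, 0.8, 0.7 or 0.5; 200 simulated studies per setting. In error standard deviations, s = 0.8 means 1/0.8 = 1.25 times as large in the noisier group, and s = 0.7 means 1/0.7 = 1.43 times. The fits used maximum likelihood as a stand-in for the Bayesian fit.

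**Tests.** (a) MNL with five attribute-by-group interactions: likelihood-ratio test on 5 df at 0.05, and whether any single interaction has |z| > 1.96. (b) Logit with one group scale parameter: test of remaining preference differences. The full interaction model has 10 parameters and the scale model 6, which leaves 4 df.

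| Scale ratio | Tasks | MNL joint test rejects | Any single interaction beyond 1.96 | Rejects once scale may differ |
|---|---|---|---|---|
| 1.0 | 8 / 12 | 6.5% / 6% | 23.5% / 24% | 5.5% / 4.5% |
| 0.8 | 8 / 12 | 57.5% / 79.5% | 84.5% / 91% | 4.5% / 5.5% |
| 0.7 | 8 / 12 | 95% / 100% | 99.5% / 100% | 3.5% / 3% |
| 0.5 | 8 / 12 | 100% / 100% | 100% / 100% | 4% / 4% |

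Every rejection in the table is false, because the preferences are identical. With 200 runs the Monte Carlo standard error is √(0.575 × 0.425 / 200) = 3.5 percentage points at 57.5%, and √(0.05 × 0.95 / 200) = 1.5 points at 5%. The 6–6.5% at equal scale is therefore compatible with the nominal 5%.

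A separate set of runs with 10 tasks and five three-level attributes gave joint rejection in 5.5%, 75.5% and 98.5% of studies at ratios 1.0, 0.8 and 0.7.

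**Odds ratios.** For the strongest attribute the formula gives exp(0.8) = 2.23 in group 1. In group 2 it gives exp(0.8 × 0.7) = 1.75 at s = 0.7 and exp(0.8 × 0.5) = 1.49 at s = 0.5. The simulated values agree (1.75–1.76 and 1.49).

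**Relative importance.** The share of the strongest attribute is 0.8 / (0.8 + 0.6 + 0.4 + 0.3 + 0.2) = 0.8 / 2.3 = 34.8%. Multiplying numerator and denominator by s leaves it unchanged. The simulation at s = 0.5 with 8 tasks gave 34.7% and 34.6%.

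**With scale modelled.** The estimated scale averaged 0.80–0.81, 0.70 and 0.50 for true values of 0.8, 0.7 and 0.5.

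**The case against.** The strongest reply is that this is loose wording. The paragraph recognises the problem and commits to dealing with it; an MNL with a scale term is sometimes still called an MNL; and details are deferred to the statistical analysis plan. Part of this stands, since that plan may well add a scale term. But the protocol does more than stay silent. It names a model for the task and, two sentences on, describes that model as assuming equal measurement. No variant is named anywhere, so an analysis plan that followed the protocol literally would inherit the error.

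Further points on the other side stand and limit the finding:

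- The distortion arises only if choice consistency differs between the groups compared. The protocol gives no evidence on how much it differs, and says only that it may.
- The simulated percentages rest on assumed designs and on a joint test that the protocol does not specify; the secondary objective asks for the extent of association.
- Relative importance, a planned output of the primary analysis, is not distorted by scale. It is not named for the subgroup comparison, however, while coefficients and odds ratios are scale-dependent.

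A reader might also infer that literacy and numeracy will be interacted with every attribute. The protocol lists them as factors to explore but does not name them as interaction terms. Nor does the text show that the primary intervals are too narrow because one patient's repeated choices are treated as independent. The protocol does not say whether patient-level terms are used, its reference to mean part-worths is compatible with them, and such structure is commonly left to the analysis plan.

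**Conclusion.** Wrong as written. The model named in Section 5.2.2 cannot control for differences in error variance, and the same paragraph says why. Used as described for the interaction analysis, it confounds choice consistency with preference.

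With identical preferences in two groups of 450, false evidence of heterogeneity appears in roughly 58–80% of studies at a scale ratio of 0.8 and 95–100% at 0.7, against about 6% at equal scale. The direction follows from the model alone. The percentages depend on the assumed number of tasks, attributes, coefficients, group split and scale ratio.

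The finding concerns coefficients, odds ratios and interaction terms in the secondary DCE analysis. It does not show that noisier patients will be misreported, because that requires consistency to differ by the covariate in question. It gives no ground for replacing the primary model.

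**What to change.** Correct the sentence in Section 5.2.2 so that it no longer credits the MNL with controlling error variance. For the secondary DCE analysis, specify one of the following:

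- **A heteroscedastic (scale-adjusted) logit** in which scale depends on the covariates under study. An identifying constraint is essential: with a full set of attribute-by-group interactions, a group scale is one parameter too many (in the example, six parameters for five group differences). Either hold one pre-specified attribute's coefficient common across groups, or test whether all coefficients are equal up to a single scale factor. The second avoids having conclusions depend on which attribute is held fixed.
- **A comparison on scale-free quantities:** ratios of coefficients, marginal rates of substitution, or relative importance computed within each group.

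Under either route, describe a difference as preference heterogeneity only if it remains after scale is allowed to differ. If the statistical analysis plan already does this, aligning the protocol sentence with it is enough.

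The cost is wording, more analysis work and somewhat wider intervals; no further data are needed. One limit remains and should be stated in the report: if one group's preferences are strictly proportional to another's, that difference cannot be told apart from a difference in scale.
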